7.8.2.1 Hematology

- Hemoglobin, WBC, absolute neutrophil count (ANC), neutrophils, platelets, lymphocytes, basophils, monocytes, eosinophils: worst CTCAE grade per patient (**Table 36**)

7.8.2.2 Biochemistry

- Serum creatinine, total bilirubin, ALT, creatinine clearance: worst CTCAE grade per patient (**Table 37**)

7.8.2.3 Other laboratory evaluations

- Pre-excision Coagulation: CTCAE grade of PT, INR, PTT (**Table 38**)
- Serum CEA: The mean and standard deviation of baseline CEA levels and the change of CEA levels from baseline at pre-excision and each follow-up visits (**Table 38**)

7.8.3 Post-operative complications

For patients with a tumour excision attempted, the following post-operative complications reported on CRF Surgery Report will be summarized (**Table 39**):

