1.2 Secondary Objectives

1. To describe the 3-year Locoregional Relapse Rate (LRR) in patients treated with organ preservation.
2. To describe the 3-year Distant Relapse Rate (DRR) in patients treated with organ preservation.
3. To describe the 3-year Disease Free Survival (DFS) rate in patients treated with organ preservation.
4. To evaluate the rate of post-operative complications following neoadjuvant FOLFOX/CAPOX and tumour excision/surgery.
5. To evaluate nature, severity and frequency of acute and long term toxicities in all patients.
6. To evaluate Quality of Life (QoL) in all patients.
7. To evaluate the cost-effectiveness of the neo-adjuvant chemotherapy approach vs. the current standard approach.

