2.0 BACKGROUND INFORMATION AND RATIONALE

Colorectal cancer is the second most common cause of cancer death in North America, with rectal neoplasms accounting for one third of incident cases. The introduction of provincial colorectal cancer screening programs has led to earlier diagnosis and 35-40% of rectal tumours present with localized disease [Jemal 2008]. Current standard therapy for T1-3 tumours includes radical surgery with Total Mesorectal Excision (TME), and preoperative chemoradiation for patients with T3 tumours or N1 tumours. Locoregional relapse rates with modern adjuvant therapy are generally 5% [Hong 2014; O'Connell 2014; Rodel 2014]. Even with laparoscopic surgery, surgical complication rates are significant and temporary diverting ostomies are associated with significant morbidity and the requirement for second surgery for reversal [Alberts 2012]. In patients treated with radical resection, ongoing issues with bowel function, incontinence, sexual function and depression persist. These are significantly worse in patients treated with neoadjuvant or adjuvant radiotherapy [Wiltink 2014].

Patients with low tumours, < 5 cm from the anal verge, commonly require permanent colostomies and the rates of non-sphincter sparing surgery in phase III trials of stage II/III rectal cancer is consistently 25% [Gerard 2012; Allegra 2014]. Loss of the rectum and a permanent colostomy has dramatic effects on quality of life, sexual/urinary and social function and at high economic cost.

Multiple single arm and randomized phase II studies have explored the use of pelvic chemoradiation (chemoXRT) followed by Transanal Endoscopic Microsurgery (TEMS) or Transanal Minimally Invasive Surgery (TAMIS) as a means to increase rectal organ preservation [Lezoche 2012]. However, even with minimally invasive surgery like TEMS/TAMIS, neoadjuvant radiation significantly increases wound-healing complications [Marks 2009] and adversely affects sphincter [Hupkens 2015] and sexual function. Furthermore, patients who develop recurrence with this strategy are difficult to salvage as radiotherapy is no longer an option. Conversely, there is virtually no prospective experience of neoadjuvant FOLFOX/CAPOX chemotherapy and excision/surgery for early rectal tumours.

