8.0 CRITERIA FOR MEASUREMENT OF STUDY ENDPOINTS

8.1 Definitions

8.1.1 *Evaluable for Organ Preservation Rate*

All patients treated with FOLFOX or CAPOX and TEMS or TAMIS will be included in the organ preservation rate analysis as primary endpoint of this study.

Organ preservation rate will additionally be calculated for all patients that have received protocol chemotherapy.

8.1.2 *Evaluable for Rectal Cancer Control*

All patients treated with FOLFOX or CAPOX and TEMS or TAMIS will be evaluated for locoregional and distant relapse rate.

Rectal cancer control will additionally be calculated for all patients that have received protocol chemotherapy.

8.1.3 *Evaluable for Disease Free Survival*

All patients treated with FOLFOX or CAPOX and TEMS or TAMIS will be evaluable for assessment of disease free survival.

Disease Free Survival will additionally be calculated for all patients that have received protocol chemotherapy.

8.1.4 *Evaluable for Post-Operative Complications*

All patients treated with FOLFOX or CAPOX and tumour excision/surgery will be evaluable for post-operative complications.

8.1.5 *Evaluable For Adverse Events*

All patients who have received at least one dose of protocol chemotherapy will be included in the safety analysis.

8.1.6 *Evaluable for Quality of Life Assessment*

All patients who have completed a quality of life questionnaire are evaluable for quality of life.

8.2 *Evidence of Disease Progression/No Response After Chemotherapy*

8.2.1 *Progression*

The diagnosis of progressive disease will be made by treating surgeon after review of the pre-excision (post-chemotherapy) MRI and endoscopy.

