APPENDIX III - DOCUMENTATION FOR STUDY

Follow-up is required for patients from the time of enrollment and will apply to all eligible and ineligible patients. This trial will use a web-based Electronic Data Capture (EDC) system for all data collection including SAE reporting (see Section 9.0 for details regarding SAE reporting). For details about accessing the EDC system and completing the on-line Case Report Forms, please refer to the Data Management Guidebook posted on the CO.28 area of the CCTG web-site (www.ctg.queensu.ca).

The ELECTRONIC CRFs to be used in this trial are:

Electronic Case Report Form	To be Completed/Submitted Electronically:	Supporting Documentation to be sent using Supporting Document Upload Tool*
BASELINE REPORT	Due within 2 weeks of patient enrollment.	Copies of signature pages of main and optional consent forms; relevant pathology & radiology reports.
CHEMOTHERAPY REPORT	To be completed after each chemotherapy cycle. Due within 2 weeks of end of cycle. This report documents treatment, adverse events and investigations for each chemotherapy cycle.	Relevant radiology reports.
PRE-EXCISION VISIT REPORT	To be complete within 2 weeks after pre-excision visit.	Relevant radiology reports.
END OF TREATMENT REPORT	To be complete within 4 weeks after final tumour excision	
SURGERY REPORT	To be complete within 4 weeks after surgery (either TME or TEMS/TAMIS)	Relevant pathology and surgery reports.
CORRELATIVE STUDIES	See Section 12 in this protocol.	Relevant pathology reports.
FOLLOW-UP REPORT	Continued follow-up after chemotherapy, radiotherapy and/or protocol tumour excision(s) completed. Due within 2 weeks after contact with patient.	Relevant pathology, radiology and surgery reports.
RELAPSE REPORT	To be completed at the time of disease relapse or failure. Due within 2 weeks after contact with patient.	Relevant pathology, radiology and surgery reports.
SHORT FOLLOW REPORT	To be completed after disease relapse or failure and for patients that have no protocol tumour excision.	
DEATH REPORT**	Required for all patients while study is open. Due within 2 weeks of knowledge of death.	Autopsy report, if done.

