4.3 Safety

The safety endpoints are post-operative complication rate, serious and non-serious adverse events (clinical and laboratory), laboratory parameters, dosing data (including dose interruptions, total delivered dose and dose modifications) and reasons off treatment.

5. Sample Size and Power

The expected organ preservation rate is 50-68% among patients with clinical T1-3N0 rectal tumours treated with chemoradiation and minimally invasive surgery. Based on these historic phase II data, the experimental treatment would be considered of no interest if the protocol specified organ preservation rate is 50% or lower (H_0) and as promising if its avoidance rate is 65% or higher (H_1).

An optimal two-stage minimax design would be used to test the above hypotheses, which would accrual 22 evaluable patients in the first stage. The trial would be stopped at the end of the first stage if the number of patients who avoided radical surgery is 10 or less. Otherwise the trial would proceed to the second stage to accrue 28 additional evaluable patients. The experimental procedure would be considered as promising if, out of the total patients accrued, 30 or more patients avoided radical surgery. The exact type I error rate and power of this design are respectively 0.1 and 0.8. Allowing for a 15% inevaluable rate, the total sample size would be 58 patients.

6. Data Set Descriptions

Five types of analysis samples will be used:

1. All Accrued Patients:

All patients accrued in the study.

2. All Chemotherapy Treated Patients:

All patients who have received at least one dose of FOLFOX or CAPOX.

3. All Chemotherapy & Excision Treated Patients

All patients who have received at least one dose of FOLFOX or CAPOX and TEMS or TAMIS.

4. All Chemotherapy & Excision/Surgery Treated Patients

All patients who have received at least one dose of FOLFOX or CAPOX and excision (TEMS or TAMIS) or surgery (TME).

5. All Quality of Life Evaluable Patients

All patients who have completed at least one quality of life questionnaire.

7. Statistical Analysis

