7.8.3.1 Reoperation

- Patients requiring reoperation: Yes, No
- Reoperation procedure performed: debridement, incision and drainage, diverting ostomy, other

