Event 1		**(**)	**(**)	**(**)	**(**)		
...							

(1) Patients may have more than one event within a category.

Table 36: Hematology: Worst Grade per Patient

Data set: All Chemotherapy Patients		Number of Patients (%) N=**
Hemoglobin		
Grade 1		** (**)
Grade 2		** (**)
Grade 3		** (**)
Grade 4		** (**)
WBC		
Grade 1		** (**)
Grade 2		** (**)
Grade 3		** (**)
Grade 4		** (**)
Absolute neutrophil count (ANC)		
Grade 1		** (**)
Grade 2		** (**)
Grade 3		** (**)
Grade 4		** (**)
Platelet		
Grade 1		** (**)
Grade 2		** (**)
Grade 3		** (**)
Grade 4		** (**)
Lymphocytes		
Grade 1		** (**)
Grade 2		** (**)
Grade 3		** (**)
Grade 4		** (**)
Basophils		
>1-1.5xULN		** (**)
>1.5-2.0xULN		** (**)
>2.0-5.0xULN		** (**)
>5.0xULN		** (**)
Monocytes		
>1-1.5xULN		** (**)
>1.5-2.0xULN		** (**)
>2.0-5.0xULN		** (**)
>5.0xULN		** (**)
Eosinophils		
>1-1.5xULN		** (**)
>1.5-2.0xULN		** (**)
>2.0-5.0xULN		** (**)
>5.0xULN		** (**)

Table 37: Biochemistry: Worst Grade per Patient

Data set: All Chemotherapy Patients	
	Number of Patients (%)
	Total N=**
Serum Creatinine	
Grade 1	** (**)
Grade 2	** (**)
Grade 3	** (**)
Grade 4	** (**)
Total bilirubin	
Grade 0	** (**)
Grade 1	** (**)
Grade 2	** (**)
Grade 3	** (**)
Grade 4	** (**)
ALT	
Grade 1	** (**)
Grade 2	** (**)
Grade 3	** (**)
Grade 4	** (**)
Creatinine Clearance	
Grade 1	** (**)
Grade 2	** (**)
Grade 3	** (**)
Grade 4	** (**)

Table 38: Other Laboratory Investigations

Data set: All Chemotherapy Treated Patients		Number of Patients (%)
		Total N=**
Pre-excision coagulation		
PT		
Grade 1		** (**)
Grade 2		** (**)
Grade 3		** (**)
Grade 4		** (**)
INR		
Grade 0		** (**)
Grade 1		** (**)
Grade 2		** (**)
Grade 3		** (**)
Grade 4		** (**)
PTT		
Grade 1		** (**)
Grade 2		** (**)
Grade 3		** (**)
Grade 4		** (**)
Serum CEA		
At Baseline		
N		**
Mean		**
Standard deviation		**
Change at pre-excision visit from baseline		
N		**
Mean		**
Standard deviation		**
Change at Month 6 follow-up visit from baseline		
N		**
Mean		**
Standard deviation		**
...		

Table 39: Surgery and Post-operative Complications

Data set: All Chemotherapy & Excision/Surgery Treated Patients		Number of patients (%) N=**
Patients Requiring Reoperation	Reoperation procedure performed	** (**)
	Debridement	**
	Incision and drainage	**
	Diverting Ostomy	**
	Other	**
Blood loss/transfusion	Estimated amount (cc) of blood loss during surgery	
	N	**
	Median	**
	Min-max	**_**
	Any transfusions or blood products during surgery	** (**)
	Type of transfusion	

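### The post-operative complication rate has no case definition or overall row, and a grade 2 surgery-related event first reported at the 30-day visit reaches no planned adverse event or complication table

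*SAP*

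**What the plan says.** Protocol 1.2 sets as its fourth secondary objective: "To evaluate the rate of post-operative complications following neoadjuvant FOLFOX/CAPOX and tumour excision/surgery". SAP 4.3 puts the rate first among the safety endpoints: "The safety endpoints are post-operative complication rate, serious and non-serious adverse events (clinical and laboratory" and so on.

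Protocol 8.1.4 fixes only the population: "All patients treated with FOLFOX or CAPOX and tumour excision/surgery will be evaluable for post-operative complications". Section 8 of the protocol does not define the event.

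The analysis is in SAP 7.8.3: "For patients with a tumour excision attempted, the following post-operative complications reported on CRF Surgery Report will be summarized". Four groups of items follow:
- reoperation, with its type ("Reoperation procedure performed: debridement, incision and drainage, diverting ostomy, other");
- blood loss and transfusion during surgery;
- intraoperative injury;
- intensive care, length of stay and discharge destination.

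The Table 39 shell repeats these items under the label "Data set: All Chemotherapy & Excision/Surgery Treated Patients".

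Protocol Appendix III makes the Surgery Report due within 4 weeks "after surgery (either TME or TEMS/TAMIS").

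SAP 7.8.1 handles adverse events separately. Those on the Chemotherapy, Pre-Excision and Surgery Reports are acute. Those on the Follow-Up and Short Follow-Up Reports are delayed.

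**The concern.** A rate needs a rule for who counts as a case. Here there is an endpoint name, a population and a list of items, but no rule that turns the items into a proportion. The analyst would have to choose the qualifying rows after seeing the data, or report no rate at all.

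The outcome also bears on the reason for the trial. Protocol 2.0 argues for leaving out radiation partly because "neoadjuvant radiation significantly increases wound-healing complications", and says that the similar chemoradiation studies have a higher surgical complication rate. A reader will look to this endpoint to see whether the chemotherapy approach does better. Wound problems managed without a return to the operating room are central to that question, and they have no row in the table that carries the endpoint's name.

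**Working it through.** The plan states no expected complication rate, threshold or precision, so there is no figure to reproduce. The check traces the endpoint through the documents.

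**1. From endpoint to output.** Protocol 1.2 and SAP 4.3 name a rate. Protocol 8.1.4 gives the population. SAP 7.8.3 gives items. Table 39 gives counts and medians for those items, with no any-complication row, overall proportion or confidence interval. SAP 7.1 already specifies exact intervals for rates, so only the quantity to which it would apply is missing.

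**2. What Table 39 can show.** Blood loss, transfusion and injury are recorded for the operation itself. Length of stay has no cut-off that would make it a complication. Reoperation, intensive care and discharge by death are post-operative outcomes. Wound events enter only through the reoperation types.

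**3. Where a surgery-related adverse event goes.**

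| First reported on | Grade | Adverse event table | Enters a complication rate? |
|---|---|---|---|
| Surgery Report | Any | Table 32 and the surgery version of Table 34 (also Table 33 if grade 3 or higher) | No |
| Follow-Up Report | 3 or higher | Table 35 | No |
| Follow-Up Report | 1 or 2 | None | No |

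The surgery version comes from the note to Table 34, which asks for the same type of table; Table 34 is an acute table.

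**4. Which form covers the 30-day visit.** SAP 7.9 takes concomitant medications at 30 days after excision from the Follow-Up Report. Protocol Appendix III uses that report for follow-up once excision is complete. Adverse events are assessed at this visit (protocol 5.0). The visit therefore falls in the lower two rows of the table above, and a grade 2 surgery-related event first reported then reaches neither Table 39 nor any adverse event table.

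**5. Dates.** 4 weeks × 7 = 28 days, and the visit is at 30 days. A Surgery Report filed on time and not later updated would not hold an event first found at the visit.

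**6. Denominators.** SAP 7.8.3 uses excision attempted. Table 39 and protocol 8.1.4 use patients treated by excision or surgery. Protocol 7.3 allows a local excision to be abandoned. A patient whose procedure was abandoned and who had no later excision is in the first set and not the second.

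**7. What the choice of rows could do (assumed counts, illustration only).** Exact 95% intervals, with 58 (all accrued) and 50 (planned evaluable) as alternative denominators:

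| Cases | Of 58 | Of 50 |
|---|---|---|
| 3 | 5.2% (1.1% to 14.4%) | 6.0% (1.3% to 16.5%) |
| 9 | 15.5% (7.3% to 27.4%) | 18.0% (8.6% to 31.4%) |
| 15 | 25.9% (15.3% to 39.0%) | 30.0% (17.9% to 44.6%) |

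Each patient added to or left out of the numerator moves the rate by 1/58 = 1.7 or 1/50 = 2.0 percentage points.

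**The case against.** The best defence is that the harms are collected and largely reported. Adverse events on the Surgery Report are graded and tabulated, and surgery-related events have their own table. Protocol 5.0 (note 18) keeps surgery-related events reportable after the 30-day visit. Severe delayed events go to Table 35. Follow-up transfusions and major medical problems go to Tables 44 and 45. The endpoint is secondary and descriptive, with no threshold and no planned formal comparison. All of this stands. It limits the point to the missing rate, the missing link between tables and the gap at grades 1 and 2, and Tables 44 and 45 do not supply a rate.

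Three stronger readings are tempting, and the documents do not support them.
- A reader might infer that wound complications are absent from Table 39. They are not: two of its reoperation types are wound or sepsis procedures. What is missing is wound events managed without reoperation.
- A reader might infer that events after 4 weeks are lost. Four weeks is a filing deadline. No section makes it an event cut-off or bars updating the form, and later severe events are tabulated.
- A reader might infer that reoperation is the only post-operative outcome in the table. Intensive care and discharge by death are there too.

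The table's title covers surgery as well as complications, so its intraoperative items belong where they are.

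**Conclusion.** The point holds in a limited form. The complication rate cannot be computed from the plan as written, because no case rule exists. The table bearing its name draws on one form and shows wound events only through reoperation. Surgery-related events below grade 3 that are first reported on the Follow-Up Report, including those from the 30-day visit, reach no planned adverse event or complication table.

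The size is unknown. The documents give no expected rate of such events and no split by grade or timing, and the counts in the working are assumptions. The conclusion about the 30-day visit rests on reading SAP 7.9 and Appendix III together, since no section states outright that this visit's adverse events go on the Follow-Up Report. The primary endpoint is not affected. The matter should be settled before the final database is analysed, because the case rule would otherwise be chosen with the results in view.

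**What to change.** Make these changes in SAP 7.8.1, 7.8.3 and Table 39:

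1. Add a first row to Table 39: the proportion of patients with any surgery-related adverse event of grade 2 or higher, reoperation or death, with an exact 95% CI. Give a second version at grade 3 or higher. Patients are the unit, as in protocol 8.1.4. Counting operations would enter a patient twice after TEMS/TAMIS then TME, and a simple binomial interval would treat the two as independent.
2. Take the events from the Surgery Report(s) and the 30-day Follow-Up Report.
3. Show the row separately after TEMS/TAMIS and after TME. For patients who have both, use the first Surgery Report for the first procedure, because note 1 to the protocol 5.0 flowsheet runs the 30-day visit from the TME date. Footnote that the first procedure then has no 30-day visit of its own.
4. Count surgery-related adverse events from the 30-day visit as acute, so that grades 1 and 2 are tabulated.
5. Use one denominator in 7.8.3 and Table 39, and say how an abandoned procedure is counted.
6. Cross-refer to the surgery version of Table 34 and to Table 35.

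The cost is SAP wording and one derived variable from forms already in use. The reported rate will be higher than a count of reoperations alone. The grade cut is a convention, and should be fixed before analysis.

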7.8.3.1 Reoperation

- Patients requiring reoperation: Yes, No
- Reoperation procedure performed: debridement, incision and drainage, diverting ostomy, other

7.8.3.2 Blood loss/transfusion

- Estimated amount (cc) of blood loss during surgery: median, minimum, maximum
- Any transfusions or blood products during surgery: Yes, no
- Type of Transfusion: Red cell concentrates, Platelets, Other

7.8.3.3 Intraoperative injury

- Any intraoperative injury: Yes, no

- Site of injury: Bladder, Ureter, Vein, Artery, Large Bowel, Small Bowel, Nerve, Other

7.8.3.4 *Hospitalization*

- Any time in intensive care: Yes, No
- Days in intensive care: median, minimum, maximum
- Ongoing hospitalization: Yes, no
- Days from admission to hospital for the tumour excision to discharge: median, minimum, maximum
- Discharge destination: Home, Assisted living (non-medical), Skilled nursing home, Hospice, Chronic care hospital, Rehabilitation facility, Died, Transfer to other hospital, Other

7.8.4 Deaths on Study/Adverse Events Leading to Discontinuations due to Toxicity

- All Deaths: number of patients who died and cause of death from CRF Death Report (**Table 40**)
- Deaths before surgery: number of patients who died and cause of death from CRF Death Report (**Table 41**)
- Adverse events leading to discontinuations of neoadjuvant: number of patients with adverse events leading to discontinuations of treatment as identified from CRF Chemotherapy Report (**Table 42**)

7.8.5 Other safety

7.8.5.1 *Sigmoidoscopy/colonoscopy*

- Sigmoidoscopy/colonoscopy during protocol treatment (reported on CRF Chemotherapy Report, CRF Pre-Excision Report, and CRF Surgery Report): all normal, at least one abnormal but all non-malignant, all abnormal and malignant (**Table 43**)
- Sigmoidoscopy/colonoscopy during follow-up (reported on CRF Follow Up all normal, at least one abnormal but all non-malignant, all abnormal and malignant (**Table 43**)

7.8.5.2 *Other radiologic investigations*

- Other radiologic investigations during protocol treatment (reported on CRF Chemotherapy Report, CRF Pre-Excision Report, and CRF Surgery Report): all normal, at least one abnormal but all non-malignant, all abnormal and malignant (**Table 43**)
- Other radiologic investigations during follow-up (reported on CRF Follow-up REPORT): all normal, at least one abnormal but all non-malignant, all abnormal and malignant (**Table 43**)

7.8.5.3 *Transfusions*

- Number of patients who received any blood transfusions (red blood cells, platelets, and/or other) during protocol treatment (reported on CRF Chemotherapy Report, CRF Pre-Excision Report, and CRF Surgery Report) (**Table 44**)
- Number of patients who received any blood transfusions (red blood cells, platelets, and/or other) during follow-up (reported on CRF Follow-Up Report) (**Table 44**)

